## Approach

To examine the efficacy of the *BSM* intervention in BF women on BNP intensity and interference and BF outcomes, we have designed an RCT with two groups: the *BSM* intervention and attention control group. An attention control group was selected to control the influence of daily reflection and bi-weekly attention for participants in the *BSM* intervention group. The self-management measures of the study were selected based on the Individual & Family Self-Management Theory pilot work by the PI regarding management of BF. Our team includes **Drs. [name] (PI), [name], and [name]** collaborated on the design of the longitudinal intervention based on their expertise in conducting longitudinal studies with maternal-infant populations. [name] is an expert in **maternal child health and with genomic, clinical, and translational methods** that are predictive of pain phenotypes. [name], statistician, is an expert related to **study design, data collection, data management, and statistical analysis**. **[name]**, geneticist at the University of Kansas Medical Center, is a long-time collaborator and is an expert in quantitative sensory testing in human subjects, **molecular/genetics methodologies** and design/implementation/statistical analyses of behavioral and **genetic data on the molecular genetics of pain**. [name], together with the Co-Is developed the current and evolving exploration of BF and BNP as a biobehavioral phenomenon. In particular, [name] pilot work (P20NR016605) tested the feasibility of the *BSM* intervention in several clinical settings with long standing relationships. The research and clinical team bring together the experience needed and through bi-weekly meetings which transitions to weekly meetings in which [name] will provide oversight of study milestones. The proposed **PROMPT RCT** expands the PI's pilot study to test the *BSM* intervention in a larger sample for efficacy testing.

[figure not shown]
There are three sub study attachments that explore additional questions based the data collection. The first attachment is the [name] Seed Grant OXTR and Maternal milk supply which with additional funding, will explore the relationship of DNA methylation of OXTR in pain insensitivity and maternal milk supply (see funded grant attachment). A second amendment is for [name], graduate student at UConn School of Nursing and key personnel on the study, who will explore the role of prolactin receptors related to milk insufficiency for her funded dissertation (see ISONG funded grant and attachment). The third attachment is for [name], key personnel on the study and honors student at UConn, will use the 6- and 24 – week interviews to explore how text-linked modules on infant development help maternal self-efficacy in taking care of their infant children.

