1	Days 1-5	Intervention Group ONLY: BL: 1 entry/ day Texts 2 times/ week breastfeeding coaching with links to Breastfeeding Modules 1-3 Maternal/Infant Care Modules 1-2	Personal computer/ smartphone	5 mins per entry  10 mins/ module	
	Days 1-5	Control Group ONLY: Texts 2 times/ week with links to Maternal/Infant Care Modules 1-2	Personal computer/ smartphone	10 mins/ module	
	Day 5	Both Groups: BB, PIS, MWB Control Group only: BL	Personal computer/ smartphone	10 mins	\$25 UConn Greenphire Gift Card or ecard
2	Days 8-12	Intervention Group ONLY: BL: 1 entry/ day Texts 2 times/ week breastfeeding coaching with links to Breastfeeding Modules 4-6 Maternal/Infant Care Modules 3-4	Personal computer/ smartphone	5 mins per entry  10mins/ module	
	Days 8-12	Control Group ONLY: Texts 2 times/ week with links to Maternal/Infant Care Modules 3-4	Personal computer/ smartphone	10 mins/ module	
	Day 12	Both Groups: BB, PIS, MWB Control Group only: BL	Personal computer/ smartphone	10 mins	\$25 UConn Greenphire Gift Card or ecard
3	Days 15-19	Intervention Group ONLY: BL: 1 entry/ day	Personal computer/	5 mins per entry	

		Texts 2 times/ week breastfeeding coaching with links to Breastfeeding Modules 7-9 Maternal/Infant Care Modules 5-6	smartphone	10mins/ module	
	Days 15-19	Control Group ONLY: Texts 2 times/ week with links to Maternal/Infant Care Modules 5-6	Personal computer/ smartphone	10 mins/ module	
	Day 19	Both Groups: BB, PIS, MWB Control Group only: BL	Personal computer/ smartphone	10 mins	\$25 UConn Greenphire Gift Card or ecard
Weeks 4-6	Days 21-40	Intervention Group ONLY: BL: 1 entry/ day Texts 2 times/ week breastfeeding coaching with links to Maternal/Infant Care Modules 7-12	Personal computer/ smartphone	5 mins per entry 5 mins/ module	
	Days 21-40	Control Group ONLY: Texts 2 times/ week with links to Maternal/Infant Care Modules 7-12	Personal computer/ smartphone	5 mins per entry	
Week 4	Day 26	Both Groups Infant development and play modules at 4 weeks	Personal computer/ smartphone	10 mins	

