#### Self-Regulation Skills and Abilities.

**Index of Self-Regulation.** The Index of Self-Regulation is an NINR common data element used across several populations which assesses an individual's general behavior and change effort to make behavioral changes and modulate thoughts, emotions, and behaviors to achieve goals.

**Breastfeeding Algorithm.** An adaptation of the LATC scale, through texted UConn Health REDCap link women will assess daily (*BSM* intervention) or weekly (attention control) infant awake/sleep state, signs of hunger, number of attempts to latch, strength of latch and of suck, pattern of pauses and sucks, and time duration of BF sessions.

**Maternal Assessment of Infant BF Behaviors.** A clinical indicator of four infant BF behaviors based on the nursing personality assessment, maternal report, and digital recording of infant BF behaviors.

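### The control arm is said to control for daily reflection, but only BSM women keep a daily log; the contrast estimates the whole BSM package and is not net of self-monitoring

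*Combined protocol and SAP*

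**What the plan says.** The Approach section gives the reason for the comparator: "An attention control group was selected to control the influence of daily reflection and bi-weekly attention".

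Table 1 (Timeline of procedures) sets out what each arm does. In week 1 the row restricted to the intervention group reads "BL: 1 entry/ day Texts 2 times/ week breastfeeding coaching with links to Breastfeeding Modules 1-3 Maternal/Infant Care Modules 1-2". The row restricted to controls reads "Texts 2 times/ week with links to Maternal/Infant Care Modules 1-2". Weeks 2 and 3 follow the same pattern. Controls complete the log only at the scheduled assessments; on Days 5, 12 and 19 the entry is "Control Group only: BL". In weeks 4–6 BSM women still log daily, and both arms get the same six care modules and two texts a week.

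Two other sections agree on the log. The Breastfeeding Algorithm entry, under Self-Regulation Skills and Abilities, has BSM women make the assessment daily, "or weekly (attention control) infant awake/sleep state, signs of hunger, number of attempts to latch". Item 8 of Protection against Risk has controls record feeding counts once a week. The Significance section lists the electronic journal as a component of BSM.

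**The concern.** An arm controls for an influence only if it receives it. If controls keep no daily log, a pain difference between arms includes whatever daily self-monitoring does to self-reported pain. A reader who relied on the Approach sentence would take a BSM benefit as net of daily reflection and attention, and so credit it to the coaching and breastfeeding content. The design cannot support that step. The pilot does not fill the gap: section 1.2 reports that BSM components examined singly were not significant.

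The attention half needs separate treatment. Text frequency is the same in both arms, but BSM texts carry coaching, follow-up contacts address breastfeeding concerns for BSM (Intervention Administration), and BSM receives more modules. The log can also generate staff contact: under item 8, a record of fewer than six feedings in 24 hours alerts the team and a nurse contacts the participant. Daily recording gives more occasions for that than weekly recording.

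**Working it through.** **The plan's own figures.** The documents state no ratio of time or attention between arms, so there is none to reproduce. The sample size does reproduce. For d = 0.39, 80% power and two-sided 0.05, n = 2(1.960 + 0.842)² / 0.39² gives 104 per arm. Allowing 25% loss, 104 / 0.75 gives 139 per arm, 278 in total against the stated 280. Nothing in that calculation depends on how the control arm is described.

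**Inputs from Table 1.** A log takes "5 mins per entry". Modules take "10 mins/ module" in weeks 1–3 and 5 minutes each in weeks 4–6. The log days are 1–5, 8–12 and 15–19, then 21–40. The table gives no time for a control log; 5 minutes is assumed, with 0 as the lower bound because the log sits inside the survey row.

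**Counts**

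| | BSM | Control |
|---|---|---|
| Log entries, weeks 1–3 | 3 × 5 = 15 | 3 |
| Modules, weeks 1–3 | 9 breastfeeding + 6 care = 15 | 6 care |
| Texts, weeks 1–6 | 2 × 6 = 12 | 2 × 6 = 12 |

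**Scheduled module and log minutes, Table 1**

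- Weeks 1–3, BSM: 15 × 10 + 15 × 5 = 225.
- Weeks 1–3, control: 6 × 10 = 60, or 60 + 3 × 5 = 75 with the logs. Ratio 60/225 = 27% to 75/225 = 33%.
- Weeks 1–3, modules alone: 60/150 = 40%.
- Weeks 1–6, BSM: 225 + 20 × 5 + 6 × 5 = 355.
- Weeks 1–6, control: 60 + 6 × 5 = 90, or 120 with six weekly logs. Ratio 25% to 34%.
- Weeks 1–6, modules alone: 90/180 = 50%.

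**The same ratio under the sections that conflict with Table 1**

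- *Log weekly after week 3* (Protection against Risk, item 6). BSM to week 6 becomes 225 + 3 × 5 + 30 = 270. Ratio 90/270 = 33% to 120/270 = 44%.
- *Surveys of 30 minutes, not 10* (Data Collection during Follow up; item 6), counted in both arms at weeks 1–3: (75 + 90)/(225 + 90) = 165/315 = 52%.
- *Eight modules of 3–5 minutes in each group* (Intervention Administration), or 24–40 minutes per arm. If all are seen by week 3: (24 + 15)/(24 + 75) = 39% to (40 + 15)/(40 + 75) = 48%. To week 6, with four control logs and daily BSM logs: (24 + 20)/(24 + 175) = 22% to (40 + 20)/(40 + 175) = 28%. On this reading module time is equal, and the log is the whole difference.

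The full range is therefore about 22% to 52%.

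**The log count under the least favourable reading.** Item 6 has the log daily for the first three weeks and also weekly from day 15. If weekly from day 15 governs, the BSM count in weeks 1–3 is 5 + 5 + 1 = 11, still against 3. No section assigns controls a daily log.

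**The case against.** The strongest reply is that the trial tests a package. SA1 asks for the effect of BSM, the journal is one of its components, and section 1.2 presents the intervention as multifactorial. Faulting the trial for not isolating one of its own ingredients would ask for a different trial. This stands: the package comparison is legitimate and randomization protects it. It does not rescue the Approach sentence, which claims a property that a package comparison does not need and this one does not have.

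Three further points have force.

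- **Attention.** The bi-weekly attention named in the sentence is matched in text frequency, so a reader who concluded that the whole sentence is false would go too far.
- **Contact time.** A reader might infer from the Table 1 minutes that controls get about a third of the contact time. The documents do not support that. The minutes are self-administered video and log time, the ratio partly restates the missing log, and it moves with whichever section is followed.
- **Daily logging in general terms.** Post Enrollment Exclusion Criteria cites missed daily entries as non-compliance for any participant, and item 6 describes the daily log without naming an arm. The week 4–6 control row in Table 1 also carries a per-entry time with no log listed. The sections that name arms are specific and agree with one another, so these are passages to reconcile, not evidence of a daily control log.

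Controls also rate pain and coping at each scheduled survey, so self-monitoring is reduced in that arm, not absent.

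**Conclusion.** The claim that the control arm controls for daily reflection is wrong as written. It fails on every section that assigns logging by arm, and the finding does not depend on any time ratio. The size is 15 scheduled log entries against 3 in weeks 1–3 under Table 1. Attention is matched in text frequency but not in content, nor in amount of material under Table 1. Control module and log time is about 27–33% of BSM time in weeks 1–3, assuming 0–5 minutes per control log and full adherence, and about 22–52% once the conflicting sections are allowed for.

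A reader might go on to infer that the primary comparison is biased or the trial underpowered. Neither follows. The contrast validly estimates BSM as a whole against a lower-intensity general-care comparator, and N = 280 is unaffected. The documents do not say how much of any effect would come from the log, so that share cannot be estimated.

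**What to change.** 1. In Approach, drop the daily-reflection claim. Suggested replacement: *The control arm receives the same number of texts through week 6 and the same general postpartum and infant-care content, but no daily log. The comparison estimates the effect of the whole BSM package (daily journal, coaching and breastfeeding modules) and is not net of self-monitoring.* Carry the same limit into the interpretation of SA1 and SA2.
2. Add one descriptive table by arm: log entries completed and modules accessed, using the REDCap access and completion counts described under Intervention Administration.
3. Reconcile Table 1, Intervention Administration, Data Collection during Follow up, Post Enrollment Exclusion Criteria and item 6 of Protection against Risk on module number and length, log frequency by arm, and survey time.

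The cost is protocol wording, one table and a slightly weaker stated inference. No endpoint, model, allocation or sample size changes. Giving controls a daily log and matched module time would support the stronger claim, but it is a trade-off: it adds burden and moves a BSM component into the comparator. Correcting the sentence does not require it.

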## 1. Preliminary Studies

[figure not shown]
**1.1. Recruitment and retention of women initiating BF.** [name] has conducted biobehavioral studies of BF using multiple methods. [name] adjusted the number of women approached to fulfill the planned enrollment based on infant gestation and study burden. For telephone and the text-based study designs, a **10 – 20% increase of the planned enrollment** met the sample size with a 90% retention of participants at 4 weeks with peak attrition at 2 weeks. Videotaping preterm and full-term infants BF and testing a BF diagnostic device prototype in the home required a **100% increase** of the planned enrollment with an 80 – 85% retention of participants at 4 weeks and peak attrition after 1 week. The pilot RCT used text communication, email, telephone contact and increasing monetary incentives to retain 94% of participants with peak attrition in 1 week.

**1.2. Randomized control trial using the BSM Intervention to decrease BNP.** The PI completed an RCT pilot study (P20NR016605, PI: [name]) to test the feasibility of the *BSM* intervention on pain intensity and BF frequency and BF exclusivity and to identify somatosensory and genetic factors that place women at risk for BNP phenotype. Our team conducted the pilot RCT at two clinical sites within **four months** including on-site data collection, web-based data entry, and follow-up text-based communication with participants (n = 65) resulting in a 94% participation retention rate. The *BSM* intervention group reported significantly lower BNP using a visual analogue scale (0 - 100) at 1 and 2 weeks. Participants' cumulative BNP (baseline +1 week, + 2 week, + 6 week, 0 - 400) was significantly different between groups at weeks 1, 2, and 6 (Figure 2). Higher Brief Pain Inventory interference scores at 1 week was predictive of increased BF self-efficacy scores at weeks 1, 2, and 6. Aligning with the literature BF self-efficacy scores correlated with BF exclusivity and at 6 weeks significantly predicted maternal well-being symptoms. Women experienced an **8.18 increase in BF and BNP scores over time with the minor allele A of rs53576 (Figure 3)**. The somatosensory testing results also showed that for every 1-unit increase in the Mechanical Detection Threshold test, women experienced 16.51 higher BNP scores and 4.82 higher BNP scores for the Windup Ratio. Six women with the *OXTR* rs2254298 minor allele experienced allodynia sensitivity. These risk factors will be examined in the larger study to determine replicability. The effect of the components of the BSM intervention on BNP were examined independently without significance which demonstrates the importance of a multifactorial approach. Participants' feedback of the *BSM* intervention included that texting was helpful while the paper-based daily journal was burdensome. All participants reported that the weekly survey completion was not burdensome.

**1.3. Maternal Assessment of Infant BF Behaviors.** Over 4 weeks, 115 BF women (38 late preterm and 77 full term) described their infants' BF behaviors which the PI analyzed using a breastfeeding

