**Justification of Sample Size:**

The sample size objective for the study is to recruit  $N = 280$  women who will be randomly assigned to the *BSM* or attention control study groups at a 1:1 ratio (140 per group). This objective provides 80% power ( $\alpha = 0.05$ , two-sided) to detect a standardized mean difference (Cohen's  $d$ ) of 0.39 or more between the *BSM* and attention control groups. It also provides 80% power to detect an odds ratio of 2.5 or more in exclusive BF between the two groups, assuming that the exclusive BF rate of the control group will be 10% higher than the national population rate in 2017 at 6, 9, 12, 18, and 24 weeks. These calculations account for "loss to follow-up" as high as 25% at 24 weeks, despite the substantially lower attrition (6%) in our pilot study. Based on our pilot study, we approached 78 women to meet our sample size of 60, with a failed screening rate of 25%. Thus, we intend to approach 374 women, which is 25% higher than our proposed study sample to meet our sample size. We anticipate that approximately 70% of the study sample will be WAHS or HHC patients.

In the pilot study, RM-ANCOVAs (with the baseline value of a measure as the covariate) revealed standardized mean differences larger than  $d = 0.39$  for the "main effect" of the intervention on BNP intensity ( $d = 0.45$ ), pain severity ( $d = 0.60$ ), cumulative pain ( $d = 0.64$ ), and BF self-efficacy ( $d = 0.48$ ) across the 1-, 2-, and 6-week time points. For BNP interference, the value of  $d$  was 0.39 at week 1, but smaller at weeks 2 and 6. Furthermore, the odds of exclusive BF in the intervention group are 2.9 times higher than the control group at 6 weeks, which is also higher than the hypothesized OR = 2.5. Therefore, we are confident that the sample size goal will be sufficiently powered to detect intervention effects on key variables for SA1 and SA2. Finally, the sample size estimate does not reflect our plans to conduct analyses based on repeated measurement of outcome variables at the 1, 2, 3, 6, 9-, 12-, 18-, and 24-week time points (due to the dearth of information regarding 24-week outcomes). Generally, the inclusion of data for an outcome variable across additional time points marginally enhances statistical power, especially for testing "main" and "interaction" effects of intervention and time.

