**SA1.** Initially, mixed effects linear modeling will be applied to contrast mean levels of pain at the 1-, 2-, and 3-week time points. The analyses will be repeated for a series of pain outcome measures, including BNP intensity, BNP interference, and cumulative BNP. The models will include “main” effects for intervention and time, an interaction between intervention and time, a random effect for “subject”, and the baseline value of the dependent variable as a covariate. Modeling results will be used to test for a time-by-intervention interaction. If the interaction is non-significant, the model will be re-fitted without it and testing will focus on the main effect of intervention. Regression diagnostics will be applied to all models to identify non-normality in residuals and potentially biasing effects of outlying observations. While mixed effects linear models are resistant to the impact of limited amounts of missing data, we will also utilize multiple imputation methods, as described below, to evaluate the sensitivity of model estimates and testing results to missing observations. Following evaluation of intervention effects at the 1-, 2-, and 3-week time points, we will proceed to assess differences in acute and cumulative BNP intensity and interference at 6, 9, 12, 18 and 24 weeks. Additionally, we will investigate whether subject-level “trends” or “growth curves” in pain levels across all eight study time points differ between the intervention and control conditions. If necessary, demographic variables will be included in the regression models both to account for potential confounding effects that might arise via imperfect randomization and to reduce unexplained between-subject variation in outcome variables.

**SA2. H2A.** We will start by investigating the intervention's effect on proportion of exclusive BF after week 6. Initially, the Pearson Chi-square test will be performed to detect the difference between intervention and control groups at 6, 9, 12, 18, and 24 weeks, respectively. Furthermore, a generalized linear mixed model with a logistic link will be applied to analyze the “main effect” of intervention and time, and “interaction effect” of intervention by time. The procedure to fit and re-fit the model will be similar to the approach for pain measures in SA1. The measure for BF self-efficacy, yield scale scores

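### SA1 pain models leave out two baseline sensory-test measures that the pilot linked to pain; pre-specifying them is a cheap, modest precision gain of unknown size.

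*Combined protocol and SAP*

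**What the plan says.** **Pilot.** Section 1.2 (under 1. Preliminary Studies) reports that "for every 1-unit increase in the Mechanical Detection Threshold test, women experienced 16.51 higher BNP scores" and gives 4.82 for wind-up ratio. The Significance paragraph on somatosensory measurement adds that greater sensitivity in the pilot predicted BNP at 1 and 2 weeks. For feeding, section 1.2 says that "BF self-efficacy scores correlated with BF exclusivity". No SD, standard error or R-squared accompanies any of these results.

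**Data collected.** Table 1 and the section on procedures at each time point schedule QST and the BSES-SF at baseline for all women.

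**SA1 model** (Data Analysis and Management). The terms are intervention, time, their interaction, a random subject effect and "the baseline value of the dependent variable as a covariate". Demographic variables may be added if needed, partly to reduce residual variation between women; none is named. The SA1 aim mentions controlling for prior breastfeeding experience, but the model description does not list it.

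**Exclusive breastfeeding (H2A).** Unadjusted chi-square tests at each visit are followed by a logistic mixed model with intervention, time and interaction. On fitting, the plan says: "The procedure to fit and re-fit the model will be similar to the approach for pain measures in SA1". No baseline predictor is named. Breastfeeding self-efficacy as an outcome follows the SA1 approach, so its baseline score is a covariate in that model.

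**SA3.** Individual QST measures are related to all outcomes over time, as an exploratory aim.

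**Randomization.** Minimization uses age, race, breastfeeding experience, expected duration, delivery route and intent to return to work. Allocation takes place before baseline data collection.

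**The concern.** Adjusting a linear model for a baseline variable that predicts the outcome reduces residual variance and corrects for chance imbalance in that variable. The plan accepts this aim but restricts the additional covariates to unspecified demographics, while the pilot points to two sensory measures that are neither demographics nor minimization factors. SA3 does not fill the gap, since it does not describe a treatment effect adjusted for QST.

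The stake is precision on the primary outcome. It is tightest for BNP interference, where Justification of Sample Size reports a pilot d of 0.39 at week 1 and smaller values at weeks 2 and 6, against a design sized for 0.39. A lesser stake is that leaving covariates to be added if needed allows a choice after the data are seen.

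For exclusive breastfeeding, borrowing the SA1 approach supplies little, because women enter within 48 hours of birth and are selected for intending to breastfeed. A baseline feeding status can carry little information.

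**Working it through.** **1. The plan's own figure.** Inputs from Justification of Sample Size: two-sided alpha 0.05, 80% power, d "of 0.39 or more between the" two groups, 140 per arm, up to 25% loss at 24 weeks.
- Completers: 140 × 0.75 = 105 per arm.
- Power at d = 0.39 with 105 per arm: 80.3% (noncentral t) or 80.7% (normal approximation).
- The t-test requirement is 105 per arm, and 105 / 0.75 = 140. The stated 280 reproduces with no covariate gain assumed.

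**2. Possible SA1 gain.** Let R² be the share of variance explained beyond the baseline outcome. Residual SD becomes √(1 − R²), so power is computed at 0.39 / √(1 − R²), the detectable difference is 0.39 × √(1 − R²), and the equivalent number of extra women is 280 / (1 − R²) − 280. The R² values are assumptions.

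| Extra R² | Power, 105 per arm (t) | Detectable d | Equivalent extra women |
|---|---|---|---|
| 0 | 80.3% | 0.390 | 0 |
| 0.02 | 81.1% | 0.386 | 6 |
| 0.05 | 82.3% | 0.380 | 15 |
| 0.10 | 84.3% | 0.370 | 31 |
| 0.15 | 86.2% | 0.360 | 49 |

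**3. What R² the pilot slopes could imply.** R² = (slope × SD of predictor / SD of BNP)². All SDs here are assumed, with a BNP SD of 20 to 30.
- Mechanical detection threshold, SD 0.1 to 0.5: from (16.51 × 0.1 / 30)² = 0.3% to (16.51 × 0.5 / 20)² = 17%.
- Wind-up ratio, SD 0.2 to 1.0: from (4.82 × 0.2 / 30)² = 0.1% to (4.82 × 1.0 / 20)² = 6%.

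These shares are before adjustment for baseline BNP, which SA1 already makes, so the extra R² is probably smaller.

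**4. How tight the margin is.** At 105 per arm, the pilot effects for intensity (d = 0.45) and cumulative pain (d = 0.64) have about 90% and 99.6% power. The 25% loss applies at 24 weeks, whereas H1 names weeks 1 to 3. At the pilot's 6% attrition (140 × 0.94, about 131 per arm), power at d = 0.39 is about 88%.

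**5. Exclusive breastfeeding.** The plan gives no numeric control rate, so 35% is assumed. Logistic regression was simulated at one visit with 105 per arm and the plan's odds ratio of 2.5 (1,500 runs, Monte Carlo error about 0.8 points). The strength of the baseline score is also assumed.

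| Odds ratio per SD of baseline score | Unadjusted power | Adjusted power |
|---|---|---|
| 1.5 | 90.8% | 92.2% |
| 1.8 | 89.5% | 92.2% |
| 2.2 | 89.7% | 94.3% |

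At control rates of 25% and 50% the gain is 0 to 3 points. Adjustment does not shrink the standard error of the log odds ratio. In a simulation at an assumed odds ratio of 2.0 and control rate of 36%, it rose from 0.284 to 0.291, 0.302 and 0.313 for covariate odds ratios of 1.5, 2.0 and 2.5. Power rises because the conditional odds ratio lies further from 1.

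**The case against.** The strongest reply is that QST was placed in SA3 on purpose. Section 1.2 says the pilot risk factors will be examined for replicability, and keeping unreplicated predictors from a pilot of 65 women out of a primary model is defensible. SA1 already adjusts for baseline pain, and nothing in the documents shows that QST adds to it. This stands as a limit on the size of the gain. It is not a reason against adjusting: a covariate that proves uninformative costs two degrees of freedom out of roughly 200.

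It is also fair to say that the covariates are not entirely free. Randomization comes before baseline collection, and Table 1 lets women complete questionnaires on their own through links. A timing rule and a missing-data rule are needed.

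A reader might go further and infer three things that the documents do not support:
- That BSES-SF enters no efficacy model. Its baseline value is a covariate in the breastfeeding self-efficacy model.
- That the pilot showed baseline self-efficacy to predict exclusivity. It reports a correlation and does not identify the score as the baseline one. The one predictive statement, in the description of the BSES-SF, concerns the 1-week score, which here falls after the intervention has begun.
- That exclusive breastfeeding has a thin power margin. A figure near 70% arises only if an odds ratio of 2.0 is substituted. At the plan's 2.5, with an assumed 36% control rate, power is about 91%.

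**Conclusion.** The point holds as a modest efficiency improvement for SA1. Two baseline measures that the pilot associated with BNP are scheduled for every woman but are absent from the primary pain models, and SA3 does not supply the adjusted treatment effect. For an assumed extra R² of 0 to 0.15, power at d = 0.39 with 105 per arm is between 80% and 86%. The lower end, no gain at all, cannot be excluded. Interference is where the gain would matter most; intensity and cumulative pain have more room if the pilot effects hold.

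The omission biases nothing and does not invalidate the sample size, which assumes no covariate gain. The exclusive-breastfeeding step is weaker. It rests on a reported correlation and an assumed covariate strength, and offers roughly 0 to 5 points of power for a conditional odds ratio.

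**What to change.** In the SA1 paragraph of Data Analysis and Management, name baseline mechanical detection threshold and wind-up ratio as covariates in the pain models, alongside the baseline outcome. State that only values obtained before any arm-specific content are used, because allocation precedes data collection. State that a missing baseline covariate is filled by simple single imputation (for example the mean over both arms combined) so that no woman is dropped.

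As an optional second step, name baseline BSES-SF in the exclusive-breastfeeding logistic mixed model under the same timing and missing-data rules, and say that the reported odds ratio is then conditional. The chi-square tests can remain as the unadjusted comparison.

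The cost is a few sentences in the plan, two degrees of freedom in SA1 and one in the logistic model, with no new data. The choice should be recorded before outcome data are examined by arm. SA3 can stay as written.
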